## Appendix B. World Medical Association Declaration of Helsinki

### Ethical Principles for Medical Research Involving Human Subjects

Adopted by the 18th WMA General Assembly, Helsinki, Finland, June 1964, and amended by the

29th WMA General Assembly, Tokyo, Japan, October 1975

35th WMA General Assembly, Venice, Italy, October 1983

41st WMA General Assembly, Hong Kong, September 1989

48th WMA General Assembly, Somerset West, Republic of South Africa, October 1996

and the 52nd WMA General Assembly, Edinburgh, Scotland, October 2000

Note of Clarification on Paragraph 29 added by the WMA General Assembly, Washington 2002

Note of Clarification on Paragraph 30 added by the WMA General Assembly, Tokyo 2004

### INTRODUCTION

1. The World Medical Association has developed the Declaration of Helsinki as a statement of ethical principles to provide guidance to physicians and other participants in medical research involving human subjects. Medical research involving human subjects includes research on identifiable human material or identifiable data.
2. It is the duty of the physician to promote and safeguard the health of the people. The physician's knowledge and conscience are dedicated to the fulfillment of this duty.
3. The Declaration of Geneva of the World Medical Association binds the physician with the words, "The health of my patient will be my first consideration," and the International Code of Medical Ethics declares that, "A physician shall act only in the patient's interest when providing medical care which might have the effect of weakening the physical and mental condition of the patient."
4. Medical progress is based on research which ultimately must rest in part on experimentation involving human subjects.

5. In medical research on human subjects, considerations related to the well-being of the human subject should take precedence over the interests of science and society.
6. The primary purpose of medical research involving human subjects is to improve prophylactic, diagnostic and therapeutic procedures and the understanding of the aetiology and pathogenesis of disease. Even the best proven prophylactic, diagnostic, and therapeutic methods must continuously be challenged through research for their effectiveness, efficiency, accessibility and quality.
7. In current medical practice and in medical research, most prophylactic, diagnostic and therapeutic procedures involve risks and burdens.
8. Medical research is subject to ethical standards that promote respect for all human beings and protect their health and rights. Some research populations are vulnerable and need special protection. The particular needs of the economically and medically disadvantaged must be recognized. Special attention is also required for those who cannot give or refuse consent for themselves, for those who may be subject to giving consent under duress, for those who will not benefit personally from the research and for those for whom the research is combined with care.
9. Research Investigators should be aware of the ethical, legal and regulatory requirements for research on human subjects in their own countries as well as applicable international requirements. No national ethical, legal or regulatory requirement should be allowed to reduce or eliminate any of the protections for human subjects set forth in this Declaration.

#### **BASIC PRINCIPLES FOR ALL MEDICAL RESEARCH**

10. It is the duty of the physician in medical research to protect the life, health, privacy, and dignity of the human subject.
11. Medical research involving human subjects must conform to generally accepted scientific principles, be based on a thorough knowledge of the scientific literature, other relevant sources of information, and on adequate laboratory and, where appropriate, animal experimentation.
12. Appropriate caution must be exercised in the conduct of research which may affect the environment, and the welfare of animals used for research must be respected.
13. The design and performance of each experimental procedure involving human subjects should be clearly formulated in an experimental protocol. This protocol should be submitted for consideration, comment, guidance, and where appropriate, approval to a specially appointed ethical review committee, which must be independent of the Investigator, the sponsor or any other kind of undue influence. This independent

committee should be in conformity with the laws and regulations of the country in which the research experiment is performed. The committee has the right to monitor ongoing trials. The researcher has the obligation to provide monitoring information to the committee, especially any serious adverse events. The researcher should also submit to the committee, for review, information regarding funding, sponsors, institutional affiliations, other potential conflicts of interest and incentives for subjects.

14. The research protocol should always contain a statement of the ethical considerations involved and should indicate that there is compliance with the principles enunciated in this Declaration.
15. Medical research involving human subjects should be conducted only by scientifically qualified persons and under the supervision of a clinically competent medical person. The responsibility for the human subject must always rest with a medically qualified person and never rest on the subject of the research, even though the subject has given consent.
16. Every medical research project involving human subjects should be preceded by careful assessment of predictable risks and burdens in comparison with foreseeable benefits to the subject or to others. This does not preclude the participation of healthy volunteers in medical research. The design of all studies should be publicly available.
17. Physicians should abstain from engaging in research projects involving human subjects unless they are confident that the risks involved have been adequately assessed and can be satisfactorily managed. Physicians should cease any investigation if the risks are found to outweigh the potential benefits or if there is conclusive proof of positive and beneficial results.
18. Medical research involving human subjects should only be conducted if the importance of the objective outweighs the inherent risks and burdens to the subject. This is especially important when the human subjects are healthy volunteers.
19. Medical research is only justified if there is a reasonable likelihood that the populations in which the research is carried out stand to benefit from the results of the research.
20. The subjects must be volunteers and informed participants in the research project.
21. The right of research subjects to safeguard their integrity must always be respected. Every precaution should be taken to respect the privacy of the subject, the confidentiality of the patient's information and to minimize the impact of the study on the subject's physical and mental integrity and on the personality of the subject.
22. In any research on human beings, each potential subject must be adequately informed of the aims, methods, sources of funding, any possible conflicts of interest, institutional affiliations of the researcher, the anticipated benefits and potential risks of the study and

the discomfort it may entail. The subject should be informed of the right to abstain from participation in the study or to withdraw consent to participate at any time without reprisal. After ensuring that the subject has understood the information, the physician should then obtain the subject's freely-given informed consent, preferably in writing. If the consent cannot be obtained in writing, the non-written consent must be formally documented and witnessed.

23. When obtaining informed consent for the research project the physician should be particularly cautious if the subject is in a dependent relationship with the physician or may consent under duress. In that case the informed consent should be obtained by a well-informed physician who is not engaged in the investigation and who is completely independent of this relationship.
24. For a research subject who is legally incompetent, physically or mentally incapable of giving consent or is a legally incompetent minor, the Investigator must obtain informed consent from the legally authorized representative in accordance with applicable law. These groups should not be included in research unless the research is necessary to promote the health of the population represented and this research cannot instead be performed on legally competent persons.
25. When a subject deemed legally incompetent, such as a minor child, is able to give assent to decisions about participation in research, the Investigator must obtain that assent in addition to the consent of the legally authorized representative.
26. Research on individuals from whom it is not possible to obtain consent, including proxy or advance consent, should be done only if the physical/mental condition that prevents obtaining informed consent is a necessary characteristic of the research population. The specific reasons for involving research subjects with a condition that renders them unable to give informed consent should be stated in the experimental protocol for consideration and approval of the review committee. The protocol should state that consent to remain in the research should be obtained as soon as possible from the individual or a legally authorized surrogate.
27. Both authors and publishers have ethical obligations. In publication of the results of research, the Investigators are obliged to preserve the accuracy of the results. Negative as well as positive results should be published or otherwise publicly available. Sources of funding, institutional affiliations and any possible conflicts of interest should be declared in the publication. Reports of experimentation not in accordance with the principles laid down in this Declaration should not be accepted for publication.

## ADDITIONAL PRINCIPLES FOR MEDICAL RESEARCH COMBINED WITH MEDICAL CARE

28. The physician may combine medical research with medical care, only to the extent that the research is justified by its potential prophylactic, diagnostic or therapeutic value. When medical research is combined with medical care, additional standards apply to protect the patients who are research subjects.
29. The benefits, risks, burdens and effectiveness of a new method should be tested against those of the best current prophylactic, diagnostic, and therapeutic methods. This does not exclude the use of placebo, or no treatment, in studies where no proven prophylactic, diagnostic or therapeutic method exists.
30. At the conclusion of the study, every patient entered into the study should be assured of access to the best proven prophylactic, diagnostic and therapeutic methods identified by the study.
31. The physician should fully inform the patient which aspects of the care are related to the research. The refusal of a patient to participate in a study must never interfere with the patient-physician relationship.
32. In the treatment of a patient, where proven prophylactic, diagnostic and therapeutic methods do not exist or have been ineffective, the physician, with informed consent from the patient, must be free to use unproven or new prophylactic, diagnostic and therapeutic measures, if in the physician's judgment it offers hope of saving life, re-establishing health or alleviating suffering. Where possible, these measures should be made the object of research, designed to evaluate their safety and efficacy. In all cases, new information should be recorded and, where appropriate, published. The other relevant guidelines of this Declaration should be followed.

---

###  Note of clarification on paragraph 29 of the WMA Declaration of Helsinki

The WMA hereby reaffirms its position that extreme care must be taken in making use of a placebo-controlled trial and that in general this methodology should only be used in the absence of existing proven therapy. However, a placebo-controlled trial may be ethically acceptable, even if proven therapy is available, under the following circumstances:

- Where for compelling and scientifically sound methodological reasons its use is necessary to determine the efficacy or safety of a prophylactic, diagnostic or therapeutic method; or

- Where a prophylactic, diagnostic or therapeutic method is being investigated for a minor condition and the patients who receive placebo will not be subject to any additional risk of serious or irreversible harm.

All other provisions of the Declaration of Helsinki must be adhered to, especially the need for appropriate ethical and scientific review.

** Note of clarification on paragraph 30 of the WMA Declaration of Helsinki**

The WMA hereby reaffirms its position that it is necessary during the study planning process to identify post-trial access by study participants to prophylactic, diagnostic and therapeutic procedures identified as beneficial in the study or access to other appropriate care. Post-trial access arrangements or other care must be described in the study protocol so the ethical review committee may consider such arrangements during its review.

9.10.2004

## Appendix C. American Urological Association Symptom Index

This section contained Clinical Outcome Assessment data collection questionnaires or indices, which are protected by copyright laws and therefore have been excluded.

**LIST OF ABBREVIATIONS**

AE	Adverse event
AED	Antiepileptic drug
ALT	Alanine transaminase (SGPT)
AST	Aspartate transaminase (SGOT)
AUA	American Urological Association
BMI	Body mass index
BP	Blood pressure
BUN	Blood urea nitrogen
CRA	Clinical monitor
CRF	Case Report Form
ECG	Electrocardiogram
ICH	International Conference of Harmonization
MedDRA ®	Medical Dictionary for Regulatory Activities
ODS	Output Delivery System
OLE	Open-label extension
PVR	Post-void Residual
QTc	QT correction
RBC	Red blood cell
SAE	Serious adverse event
SAP	Statistical analysis plan
SAS ®	Statistical Analysis Software
SD	Standard deviation
TEAE	Treatment-emergent adverse event
TID	Three time a day
WBC	White blood cell
WHO	World Health Organization

## 1 INTRODUCTION

Epilepsy is among the most common neurological disorders, affecting approximately 50 million people worldwide. Classical antiepileptic drugs (AEDs) currently provide satisfactory seizure control in approximately 70% of patients; however, the remaining 30% of epilepsy patients are refractory to treatment. The partial onset seizure is the most common type of seizure that is uncontrolled in adult patients. The introduction of new AEDs (e.g., vigabatrin, lamotrigine, gabapentin, topiramate, levetiracetam, oxcarbazepine, zonisamide, and felbamate) during the last decade has increased therapeutic possibilities. However, data from recent clinical trials demonstrate that none of the newer AEDs provides adequate seizure control in all patients. The treatment of patients that do not respond to current AEDs remains a problem and motivates the continued search for compounds with high antiepileptic potential and low rates of side effects.

Retigabine (GKE-841 or D-23129), N-[2-amino-4(4-fluorobenzylamino)-phenyl] carbamic acid ethyl ester, is a new chemical entity discovered by ASTA Medica, Germany, and was acquired by Valeant Research & Development (Valeant) for development as an AED for the treatment of partial onset seizures. It is a deaza analog of flupirtine, currently marketed in some regions as a centrally acting analgesic with ancillary muscle relaxing properties.

Two Phase 3 studies (VRX-RET-E22-301 and VRX-RET-E22-302) to compare the efficacy and safety of retigabine (600 mg/day, 900 mg/day, or 1200 mg/day) to placebo as an adjunctive therapy in refractory patients with partial-onset seizures are currently being conducted. These studies are randomized, double-blind, placebo-controlled, multicenter, parallel-group trials enrolling a total of approximately 790 patients, globally. Because of the serious nature of epilepsy, the retigabine clinical program had foreseen that all patients who enter and complete a Phase 3 study with retigabine will be given the opportunity to continue treatment, if they consent and if the Principal Investigator feels they can benefit from continued retigabine treatment. Hence, an open-label extension protocol was designed for each double-blind study.

This study is the open-label extension of the Phase 3 Study VRX-RET-E22-302. VRX-RETE22-302 is a randomized, double-blind, placebo-controlled, parallel-group, multicenter, study of 900 mg/day and 600mg/day retigabine versus placebo. During the 4-week titration phase patients are titrated to the target dose. 510 patients are expected to be randomized to treatment. A 12-week maintenance phase follows. All patients who wish to enter the open-label extension protocol will enter a 4-week transition phase in which their dose will be titrated to 300 mg TID in order to maintain the blind to the maximum extent. Thereafter, the patients could enter this extension study (Study VRX-RET-E22-304). Patients who do not wish to enter the open-label extension protocol will have their dose tapered over a 3-week period.

This Statistical Analysis Plan (SAP) was created according to Protocol VRX-RET-E22-304, Amendment 1 (July 2, 2007).

## 2 STUDY OBJECTIVES

### Primary Objective

To evaluate the safety and tolerability of long-term therapy with retigabine administered as adjunctive therapy in adult epilepsy patients with partial-onset seizures, who completed the double-blind Study VRX-RET-E22-302.

### Secondary Objective

To evaluate efficacy of long-term treatment with retigabine and patient quality of life, evaluated through the QOLIE-31-P questionnaire.

## 3 INVESTIGATIONAL PLAN

### 3.1 Overall Study Design and Plan

This is an open-label extension study of the placebo controlled, double-blind Study VRXRET-E22-302. Patients will be treated with 600 - 1200 mg/day of retigabine as an adjunct therapy to their current antiepileptic medications (AEDs) or vagal nerve stimulation as established in Study VRX-RET-E22-302. Following completion of the Transition Phase of the double-blind study (Study VRX-RET-E22-302), treatment in this open-label extension study will be continued until retigabine is approved and commercially available, or until the program is discontinued, followed by a 3-week tapering period and a 30 day post-study period for collection of adverse events.

### 3.2 Efficacy and Safety Variables

A study flow chart summarizing all study procedures can be found in Table 1.

#### 3.2.1 Efficacy Assessments

Patients will keep a seizure diary throughout the study. The anticonvulsant efficacy of retigabine will be evaluated by comparison of baseline seizure frequency (obtained during the 8-week baseline period of Study VRX-RET-E22-302) with seizure frequency obtained during retigabine therapy in this open-label extension study (VRX-RET-E22-304). The primary efficacy variable is the percentage change in the monthly seizure rate from the baseline phase to the open-label treatment phase. The proportion of responders (patients experiencing  $\geq 50\%$  reduction in seizure frequency) from baseline to the open-label treatment phase will be evaluated.

**Table 1: Study Flow Chart**

Study Procedures	Baseline 	Open-Label Extension-First Year 									Open-Label Extension-Second Year and Onward 					
	0	1	1a 	2	2a 	3	3a 	4	4a 	5 	6	7	8 	9	10	11 
Month in Study	0	1	2	3	4	6	8	9	10	12	16	20	24	28	32	36
Eligibility /ICF	X															
Physical & Neuro Exam	X									X			X			X
Brief Neuro Exam		X		X		X		X			X	X		X	X	
Vital Signs (BP,HR,&Temp) &Wt 	X	X		X		X		X		X	X	X	X	X	X	X
12 Lead ECG	X	X		X		X		X		X			X			X
Blood Chem and Hematology	X	X		X		X		X		X	X	X	X	X	X	X
Hematological Evaluation			X		X		X		X							
Urinalysis (including Microscopy)	X	X		X		X		X		X	X	X	X	X	X	X
AUA Symptom Index 	X	X		X						X						
PVR Bladder Ultrasound	X	X		X						X						
Serum Preg Test 	X									X			X			X
Urine Preg Test 	X															
Seizure Diary Review	X	X		X		X		X		X	X	X	X	X	X	X
AE Evaluation	X	X		X		X		X		X	X	X	X	X	X	X
Concomitant Medication	X	X		X		X		X		X	X	X	X	X	X	X
QOLIE-31-P Qx	X			X		X		X		X			X			X
Dispense OLE Study Meds 	X	X		X		X		X		X	X	X	X	X	X	X
Collected Returned OLE Study Meds		X		X		X		X		X	X	X	X	X	X	X

8

CONFIDENTIAL  
RM2009/00475/00  
VRX-RET-E22-304

**Table 1: Study Flow Chart (continued)**

1. Baseline for the open-label extension study corresponds to the assessments performed at the last visit of the Maintenance phase (Visit 9) of Study VRX-RET-E22-302 for all patients. The final, baseline eligibility assessment for the open-label extension study, including obtaining informed consent and dispensing open-label study medication will be performed at the last visit of the Transition phase (Visit 11) of Study VRX-RET-E22-302.
2. Study Visit 1 will have a window range of  $\pm 3$  days. After Study Visit 1, all remaining study visits will have a window range of 7 days around that visit day to accommodate individual schedules. Each study month will be defined as 30 calendar days. If a patient visit occurs outside the visit window, the study clinical monitor (CRA) should be notified and the reason for the deviation noted. An attempt should be made to ensure that the patient returns for subsequent visits on schedule using the last visit of the Transition phase (Visit 11) of Study VRX-RET-E22-302, which corresponds to the final, Baseline eligibility visit for the open-label extension study.
3. This open-label extension study will be continued until retigabine is approved and commercially available, or until the program is discontinued, followed by a 3-week tapering period and a 30 day post-study period for collection of adverse events. After the first year, the study visits will occur every 4 months (3 visits per year). After the first year, the assessments for the first 2 study visits of each year (e.g. Visits 6, 7, 9 and 10) will be identical, and the assessments for the last study visit of each year (e.g. Visits 8 and 11) will be identical.
4. All patients who discontinue early from study treatment during the open-label extension study will have their study medication tapered over a 3-week period, reducing their daily dose by one third per week, and then return for a final visit. Patients who discontinue early during the first year of the open-label extension study will complete all assessments and evaluations scheduled for Study Visit 5. Patients who discontinue early during the second year of the open-label extension study will complete all assessments and evaluations scheduled for Study Visit 8. Patients who discontinue early during the third year of the open-label extension study will complete all assessments and evaluations scheduled for Study Visit 11. Also, all adverse events should be followed and collected up to until 30 days after administration of the last dose of study drug (end of study drug taper-off).
5. Supine and standing blood pressure, heart rate.
6. In addition to the scheduled pregnancy tests, a pregnancy test should be performed during the study whenever a woman's menstrual period is 5 days late.
7. The AUA Symptom Index and the PVR bladder ultrasound will only be performed during the first year of the open-label extension study (Visits 1, 2, and 5).
8. Dispensation of study medication is not applicable at the final study visit, if a patient has discontinued early or completed the open-label extension study.
9. Study visits added per FDA comments that the open label extension trial should include more frequent hematological monitoring. These are now in-line with the hematological monitoring frequencies per the VRX-RET-E22-302, double-blind trial.

6

CONFIDENTIAL

RM2009/00475/00  
VRX-RET-E22-304

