### **10.5. Baseline**

Except for final study eligibility, informed consent and dispensation of open-label extension study medication, the Baseline assessments for the open-label extension study correspond to the assessments performed at the last visit of the Maintenance phase (Visit 9) of Study VRX-RET-E22-302 (See Study Flow Diagram - Appendix A). After completion of all study procedures on the last visit of the Transition phase (Visit 11) of Study VRX-RET-E22-302, patients will be allowed to enter this open-label extension study (VRX-RET-E22-304). All ongoing AEs and concomitant medications at the last visit of the Transition Phase (Visit 11) of Study VRX-RET-E22-302 will need to be transferred and captured on the appropriate open-label extension AE and Concomitant Medication CRF pages. The final study eligibility and informed consent for the open-label extension study should be performed at the last visit of the Transition phase (Visit 11) of Study VRX-RET-E22-302. A urine pregnancy test will be performed on female patients of child-bearing potential, to immediately confirm the non-pregnancy eligibility requirements to enter the VRX-RET-E22-304 study. After confirmation of all final study eligibility requirements and obtaining proper informed consent, open-label study medication (sufficient supply of bottles at appropriate dose strengths = 50 mg, 100 mg, 300 mg) will be dispensed to patients, along with seizure diaries for completion until the next study visit (Visit 1 / Month 1).

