#### 4.4 Efficacy Evaluation

“Monthly total partial seizure” as well as “monthly total seizure” rates will be calculated for the entire open-label part of Study VRX-RET-E22-304 and statistically described. “Monthly total partial seizure” rate is defined as the sum of total partial seizures throughout the open-label portion (of Study VRX-RET-E22-304), divided by open-label duration in days, standardized by 28 days (1 month). “Monthly total seizure” rate is defined as the sum of partial and generalized (or unclassified) seizures throughout the open-label duration in days, standardized by 28 days (1 month).

Monthly total partial seizure rates observed during the open-label extension period will be compared to the monthly total seizure rates observed during the Baseline phase of the double-blind study VRX-RET-E22-302. The baseline monthly total seizure rates will only be derived for patients who enter this open-label extension and have a monthly total partial seizure rate during the open-label extension period. The percent change in monthly total partial seizure rates from the Baseline phase will be classified into <0, [0, 25), [25, 50), [50, 75), [75, 100] with a description of the frequencies. The responder rate during the open-label study (defined as a reduction in seizure frequency  $\geq 50\%$ ) will also be summarized using descriptive statistics.

The monthly total partial seizure rates compared to the baseline monthly total partial seizure rate will be presented cumulatively for each timepoint (months 1, 3, 6, 9, 12, 16, 20, 24, 28, 32 and 36) during the open label extension period and separately for eleven cohorts of patients treated with retigabine for at least 1, 3, 6, 9, 12, 16, 20, 24, 28, 32 and 36 months. In each cohort, patients will be followed for entire indicated duration of treatment. For example, patients in the 36-month cohort will also be part of the shorter-duration cohorts.

A similar analysis will be repeated for the responder rate during the open-label study.

A plot of the median percent reduction from baseline in seizure frequency over time by duration of treatment will also be produced.

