#### 4.5.5.4 AUA Symptom Index

An AUA Symptoms Index, a 7-item Likert-scored scale describing urinary bladder function, is completed by the investigator at the baseline phase, and at Months 1, 3 and 12.

Descriptive statistics (n, mean, std, median, minimum, maximum) of the AUA symptom index scores in each treatment group will be presented by two table layouts: 1) AUA raw overall scores at baseline, Months 1, 3 and 12, 2) change from baseline to Month 1, 2 and 12.

Besides the descriptive statistics tables, AUA symptom index scores will be categorized by using 3 levels: 0-7 as mild, 8-19 as moderate, and >19 as severe. A shift table of the number (%) of patients in the categories of mild, moderate, and severe will be provided.

A listing of AUA symptom index data will be provided.

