STD	xxx.xx		
MEDIAN	xxx.x		
MINIMUM	xxx		
MAXIMUM	xxx		
OPEN-LABEL PHASE			
N	xxx	xxx	xxx
MEAN	xxx.x	xxx.x	xxx.x
STD	xxx.xx	xxx.xx	xxx.xx
MEDIAN	xxx.x	xxx.x	xxx.x
MINIMUM	xxx	xxx	xxx
MAXIMUM	xxx	xxx	xxx

42

CONFIDENTIAL

RM2009/00475/00  
 VRX-RET-E22-304

Valeant Pharmaceuticals North America  
Protocol Number: VRX-RET-E22-304

PAGE X OF X

FOOTNOTE:

[1] BASELINE PHASE IN STUDY VRX-RET-E22-302

43

CONFIDENTIAL

RM2009/00475/00  
VRX-RET-E22-304

---

Program Path/sas program name

Run Date:

---

Filename: 87272\_304\_SAP\_v2\_final

page 42 of 148

Valeant Pharmaceuticals North America  
 Protocol Number: VRX-RET-E22-304

PAGE X OF X

TABLE 9.1 PERCENTAGE CHANGE IN MONTHLY TOTAL PARTIAL SEIZURE FREQUENCY FOR PATIENTS TREATED WITH RETIGABINE FOR AT LEAST 1 MONTH DURING THE OPEN-LABEL EXTENSION SAFETY POPULATION

STATISTICS	RETIGABINE (N=XXX)		
	OBSERVED	CHANGE FROM BASELINE	PERCENTAGE CHANGE FROM BASELINE
BASELINE [1]			
N	xxx		
MEAN	xxx.x		
STD	xxx.xx		
MEDIAN	xxx.x		
MINIMUM	xxx		
MAXIMUM	xxx		
MONTH 1			
N	xxx	xxx	xxx
MEAN	xxx.x	xxx.x	xxx.x
STD	xxx.xx	xxx.xx	xxx.xx
MEDIAN	xxx.x	xxx.x	xxx.x
MINIMUM	xxx	xxx	xxx
MAXIMUM	xxx	xxx	xxx

44

CONFIDENTIAL

RM2009/00475/00  
 VRX-RET-E22-304

Program Path/sas program name

Run Date:

Valeant Pharmaceuticals North America  
Protocol Number: VRX-RET-E22-304

PAGE X OF X

FOOTNOTE: [1] BASELINE PHASE IN STUDY VRX-RET-E22-302

45

CONFIDENTIAL

RM2009/00475/00  
VRX-RET-E22-304

---

Program Path/sas program name

Run Date:

---

Filename: 87272\_304\_SAP\_v2\_final

page 44 of 148

Valeant Pharmaceuticals North America  
 Protocol Number: VRX-RET-E22-304

PAGE X OF X

TABLE 9.2 PERCENTAGE CHANGE IN MONTHLY TOTAL PARTIAL SEIZURE FREQUENCY FOR PATIENTS TREATED WITH RETIGABINE FOR AT LEAST 3 MONTHS DURING THE OPEN-LABEL EXTENSION SAFETY POPULATION

STATISTICS	RETIGABINE (N=XXX)		
	OBSERVED	CHANGE FROM BASELINE	PERCENTAGE CHANGE FROM BASELINE
BASELINE [1]			
N	xxx		
MEAN	xxx.x		
STD	xxx.xx		
MEDIAN	xxx.x		
MINIMUM	xxx		
MAXIMUM	xxx		
MONTH 1			
N	xxx	xxx	xxx
MEAN	xxx.x	xxx.x	xxx.x
STD	xxx.xx	xxx.xx	xxx.xx
MEDIAN	xxx.x	xxx.x	xxx.x
MINIMUM	xxx	xxx	xxx
MAXIMUM	xxx	xxx	xxx
MONTH 3			
N	xxx	xxx	xxx
MEAN	xxx.x	xxx.x	xxx.x
STD	xxx.xx	xxx.xx	xxx.xx
MEDIAN	xxx.x	xxx.x	xxx.x
MINIMUM	xxx	xxx	xxx
MAXIMUM	xxx	xxx	xxx

46

CONFIDENTIAL

RM2009/00475/00  
 VRX-RET-E22-304

Program Path/sas program name

Run Date:

Valeant Pharmaceuticals North America  
Protocol Number: VRX-RET-E22-304

PAGE X OF X

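### With Study 302 Visit 9 as baseline and one pooled column, the safety and quality-of-life change tables average two different quantities, depending on former arm

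*SAP*

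**What the plan says.** SAP Table 1, the visit schedule, has a Baseline column covering vital signs and weight, ECG, laboratory tests, urinalysis, AUA, PVR and QOLIE-31-P. Its footnote 1 reads: "Baseline for the open-label extension study corresponds to the assessments performed at the last visit of the Maintenance phase (Visit 9") of Study 302, for all patients. Protocol 10.5 says that "the Baseline assessments for the open-label extension study correspond to the assessments performed at the last visit of the Maintenance phase (Visit 9"), and Protocol 10.1 and Appendix A agree.

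SAP 1 gives the timing of Study 302, which compared 600 mg/day, 900 mg/day and placebo: "During the 4-week titration phase patients are titrated to the target dose"; "A 12-week maintenance phase follows"; and patients who want to continue "will enter a 4-week transition phase in which their dose will be titrated to 300 mg TID".

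SAP 4.5.4, 4.5.5 and 4.6 ask for change from baseline, a shift, or a change category, and name no visit for that baseline. The shells (Tables 22, 24, 25, 29, 30, 31, 36, 38, 40 and 43) each have a single RETIGABINE heading and no split by former Study 302 arm.

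Efficacy is handled differently. SAP 4.4 uses rates "observed during the Baseline phase of the double-blind study VRX-RET-E22-302", and the shells for Tables 8, 9.1 and 9.2 carry the footnote "BASELINE PHASE IN STUDY VRX-RET-E22-302". The safety and QoL shells have no such footnote.

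**The concern.** Safety is the primary objective. Someone reading a mean change from baseline in an extension report will take it as the change on retigabine. With Visit 9 as baseline, that holds for former placebo patients only. For former retigabine patients the same column shows only what arose after week 16. The pooled mean is a mixture of the two, with weights set by how many patients came from each arm, and the shells give no way to separate them. The affected outputs include PVR change and the AUA shift, which bear on the bladder effects that Protocol 10.3.4 singles out for careful attention.

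The SAP also does not settle which baseline applies, so two programmers could follow it and produce different tables.

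**Working it through.** The plan has no figure of its own to reproduce: Protocol 11.3 calls sample size not applicable, and the planned summaries are descriptive. The check is therefore the timing, the mixture, and a comparison of the baseline texts.

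**Timing.** Inputs: titration 4 weeks, maintenance 12 weeks, transition 4 weeks (SAP 1); a study month of 30 days (Protocol 10.1).
- Visit 9: 4 + 12 = 16 weeks, or 112 days, of double-blind treatment.
- Month 1, former placebo: at most 28 + 30 = 58 days on drug; 58/7 = 8.3 weeks.
- Month 1, former retigabine: 112 + 28 + 30 = 170 days; 170/7 = 24.3 weeks.

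The 16-week difference in exposure persists in every later row.

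**What the pooled change shows.** Let p be the former-placebo share of enrolled patients and f the fraction of the drug effect already present at Visit 9 in former retigabine patients. The documents give neither; both are assumed. For an effect that does not depend on dose:

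visible share = p + (1 − p)(1 − f) = 1 − (1 − p)f

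| p | f | visible share |
|---|---|---|
| 1/3 | 0 | 100% |
| 1/3 | 0.5 | 67% |
| 1/3 | 0.75 | 50% |
| 1/3 | 1 | 33% |
| 0.20 | 1 | 20% |
| 0.50 | 1 | 50% |

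If the effect is linear in dose, the two retigabine arms are of equal size, and everyone takes dose D in the extension, the share is 1 − (1 − p)f(600/D + 900/D)/2. With p = 1/3 and f = 1:
- D = 600: 1 − (2/3)(1.25) = 16.7%
- D = 900: 1 − (2/3)(0.833) = 44.4%
- D = 1200: 1 − (2/3)(0.625) = 58.3%

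**Do absolute categories replace the change?** Not fully. Two invented patients show why.
- QTcF 400 msec before Study 302, 425 at Visit 9, 435 at Month 12. The change is 435 − 425 = 10 from Visit 9 (category up to 30) but 435 − 400 = 35 from pre-treatment (category 30 to 60). Table 28 shows at most 450 throughout.
- Weight 70, 73 and 76 kg at the same times. 76/73 is +4.1%, below the 7% flag of Listing 26; 76/70 is +8.6%, above it.

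**Which baseline does the SAP mean?**
- For Visit 9: Table 1 footnote 1 and the three Protocol locations. No other text names a visit for these assessments.
- For a pre-treatment reference: SAP 4.3 sets Day 0 at the start of Study 302 treatment, and Listing 3 labels its baseline date as Day 0, in a column separate from the extension start date. SAP 4.5.5.4 says the AUA "is completed by the investigator at the baseline phase, and at Months 1, 3 and 12", and SAP 4.6 uses the same baseline-phase term for QOLIE-31-P; SAP 4.4 uses that term for the pre-treatment phase of Study 302.
- Unclear: the label BASELINE AVG in Tables 27 and 28 is not explained. Weight is taken before Study 302 treatment in the SAP 4.2 summaries, but it is also a vital sign in SAP 4.5.5.1, where no baseline is named.

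**The case against.** The strongest reply is that footnote 1 belongs to a visit schedule and says which visit fills a column; it does not say that change is calculated from there. Day 0 in SAP 4.3 and Listing 3 points to the start of Study 302 treatment. If programmers use that, the loss in former retigabine patients does not arise. This stands as a limit: Visit 9 is the only explicit definition, but a contested one. It does not remove the point, because following the plan's one explicit definition gives the mixture above.

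Second, a reader might infer that effects present by week 16 are left out of the safety report. The documents do not support that. They are absent from the former retigabine patients' own change, but only diluted in the pooled change. Observed values by visit remain, as do absolute categories for QTc, liver tests, PVR, AUA and orthostatic hypotension. Only the baseline rows of those tables depend on the choice.

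Third, change since entry to an extension is a legitimate question, and the first 16 weeks fall within Study 302's controlled period. The Protocol synopsis also plans a comparison with Study 302 and combined TEAEs. That supports keeping change from Visit 9. But the SAP does not carry the comparison forward, and combined TEAEs supply no laboratory, ECG or PVR change from before treatment.

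**Conclusion.** The point holds, conditional on Visit 9 being used: ten tables, plus the change-based entries in Listings 25 and 26, then rest on a baseline that is pre-drug for one former arm and about 16 weeks into drug for the other two. Former placebo patients' change, effects arising after week 16, observed post-baseline values, absolute categories and seizure efficacy are not affected.

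The size cannot be known from the documents. One third visible is an illustration for a dose-independent effect complete by week 16 with an assumed one-third former-placebo share; the other assumptions shown run from 17% to no loss at all.

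A reader might also infer that the QTc withdrawal criterion (Protocol 10.20.1, SAP 4.1.1) contradicts Table 29 and Listing 25. No two passages conflict: the criterion takes whichever baseline is defined, and the passages should agree. Nothing here bears on what that criterion should be.

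**What to change.** In SAP 4.5.4, 4.5.5 and 4.6:
- State the baseline for all safety and QoL change, shift and change-category outputs, and name the visit in place of the baseline-phase wording.
- Show these outputs by former Study 302 arm (placebo, retigabine) and overall. This also meets SAP 4.5.5.4, which promises AUA statistics by treatment group that the single-column shell cannot deliver.
- Alongside change from Visit 9, show change from the last value before first retigabine dose: the Study 302 pre-treatment value for former retigabine patients where one was collected, and Visit 9 for former placebo patients.
- Footnote the baseline on each affected shell, explain BASELINE AVG, and state which weight baseline Table 31 and Listing 26 use.

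The cost is a merge of Study 302 records, which SAP 4.2 already draws on for baseline characteristics, and extra columns in about ten descriptive tables and two listings. No alpha or power is involved. Reported changes may look less favourable. The documents do not say whether Study 302 collected PVR, AUA and QOLIE-31-P before treatment; where it did not, only the former-arm split is possible.
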